anticipate increased risks for a fistula or other surgical complications, beyond those seen with a primary surgical resection. Furthermore, because the irradiated tumor and surrounding lung tissue are resected with the lobectomy, we do not foresee increased toxicity from combined SBRT and pembrolizumab treatment.

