4.2 Rationale

4.2.1 Rationale of the trimodality approach

As stated in section 4.1.1, despite the promising results of SBRT, overall survival was not different between the two modalities and the relapse rate is still substantial. In a study by Senthil et al, 676 patients underwent SBRT for early stage lung cancer with a 2-year recurrence rate of 22% (6). Furthermore, of the 124 recurrences, 82 (66%) were distant recurrences. Looking at the preclinical and clinical data on the synergistic systemic antitumor effect of combination radiotherapy and immunotherapy, there is a strong biological rationale

to study these two modalities together as induction therapy for patients with operable early stage NSCLC.

In this protocol we will explore the addition of immunotherapy to SBRT to augment the antitumor T cell response, already associated with radiotherapy. This exploratory study aims primarily to assess the safety of the trimodality treatment strategy and to identify and characterize the immunological mechanisms of action of combined SBRT and anti-PD-1 treatment. Because the SBRT technique allows to irradiate small tumor volumes with maximal sparing of healthy lung tissue, this is the ideal and safest setting to introduce the combination of pulmonary radiotherapy and immunotherapy in lung cancer. The results of this study can serve as a proof of principle for the immunological effect of thoracic radiotherapy in general and might serve as a vehicle for further development of the combination of radiotherapy and immunotherapy in early stage lung cancer and stage III disease, a setting where radiation pneumonitis is a well-known and feared complication.

Because surgical resection is still the current standard of care for these patients, the subjects will undergo a lobectomy with hilar and mediastinal lymph node dissection after SBRT and pembrolizumab treatment. This is a key feature of this study and an unique opportunity to perform histological examination of the entire lung tumor and lymph nodes after immunotherapy, allowing to examine immune response heterogeneity and to correlate this with the non-invasive imaging and blood results. In the surrounding normal lung tissue, radiation and immunotherapy induced toxicity can be evaluated.

The goal of this study is to evaluate the safety and mechanisms of action of the novel trimodality treatment approach.

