4.2.4 Rationale for Endpoints

This an exploratory study that aims to evaluate the safety of the trimodality approach and characterize the immunological mechanisms of action of combination radiotherapy and immunotherapy. Therefore the primary endpoints of this study are the tolerability and toxicity of combined SBRT +/- pembrolizumab treatment and surgery and to analyze the immunological antitumor response. The endpoints will be assessed by clinical signs of

radiation pneumonitis and examination of tumor core biopsies and resection material, FACS analysis on EBUS-FNA of TDLNs and peripheral blood to detect immunomodulation.

Secondary endpoints are the correlations of *in-vivo* PD-1 expression, quantified by immune-PET, with tissue and blood based immune-parameters.

The levels of PD-1 and PD-L1 expression are variable over time (see section 4.1.8) and expression has been found to be heterogeneous between and within tumor lesions of the same patient. The biomarker PD-L1 IHC is currently being validated in multiple clinical studies to stratify patients based on the intensity and percentage of positive staining. This trial is a unique opportunity to study the 3-dimensional uptake of ⁸⁹Zr-pembrolizumab in the tumor and correlate the imaging result with the 3D immunohistochemistry results of the surgical tumor specimen.

Although pneumonitis will be assessed as a symptom, an exploratory objective is to evaluate radiation induced changes to healthy lung tissue after SBRT +/- pembrolizumab treatment in the resected lung lobe.

The number of patients (n=10 in each arm) is too low to correlate study parameters to clinical outcome in terms of progression-free or overall survival.

4.2.5 ⁸⁹Zr-pembrolizumab imaging

To identify patients that will benefit the most from treatment with mAbs like pembrolizumab, better knowledge of the *in vivo* behavior of the drug is warranted. For this, positron emission tomography (PET) imaging with radiolabeled mAbs (immuno-PET) is an attractive option.

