6.0 TRIAL FLOW CHART

6.1 Study Flow Chart

Trial period	Screening Phase	Imaging	Induction treatment phase	Surgery	Follow-up
Scheduling Window (Days)	-30 to -1	-14 to 0	From day 1 to day 56 (2 weeks after 2 nd pembrolizumab cycle)	From day 56 to day 70	From surgery to 6 months thereafter
Administrative Procedures					
Informed Consent	X				
Eligibility Criteria	X				
Demographics and Medical History	X				
Prior and Concomitant Medication Review	X				
PET Imaging					
⁸⁹ Zr-pembrolizumab		X ^a			
Clinical Procedures/Assessments					
Review Adverse Events	X		X ^b		
Full Physical Examination	X				
Directed Physical Examination	X		X ^b		X ^c
Vital Signs and Weight	X		X ^b		
ECOG Performance Status	X		X ^b		
12-lead ECG	X				
¹⁸ F-FDG PET-CT		X		X	
Laboratory Procedures/Assessments					
Pregnancy Test	X				
Complete Blood Count (CBC)	X	X ⁱ	X ^b		
Comprehensive Serum Chemistry Panel	X		X ^b		
Urinalysis	X				
T3, FT4 and TSH	X		X ^d		
Treatment					
SBRT			X		
Pembrolizumab			X ^a		
Surgery				X	
Efficacy Measurements					
Tumor Imaging (CT thorax +/- abdomen and MRI brain)		X	X ^e		X ^f
Tumor Tissue and Blood analysis					
Core tumor biopsy	X				
EBUS FACS		X	X ^g		
Surgical resection specimen				X	
Immunophenotyping		X ^h	X ^h	X ^h	X ^h

X^a: only for patients randomized to the SBRT + pembrolizumab arm; X^b: every cycle; every 6 weeks; X^c: if indicated; X^d: after 2nd pembrolizumab cycle; X^e: within 2 weeks of surgery; X^f: following resection every 3 months for the first 2 years and every 6 months for the 3 years thereafter; X^g:; X^g:between week 2 and 3 after SBRT; . X^h: see section 7.1.2.10 for timepoints; Xⁱ: 72 and 144 hours post-injection for patients undergoing ¹⁸F-FGD-PET-CT

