7.2 Assessing and Recording Adverse Events

An adverse event is defined as any untoward medical occurrence in a patient or clinical investigation subject administered a pharmaceutical product and which does not necessarily have to have a causal relationship with this treatment. An adverse event can therefore be any unfavorable and unintended sign (including an abnormal laboratory finding, for example), symptom, or disease temporally associated with the use of a medicinal product or protocol-specified procedure, whether or not considered related to the medicinal product or protocol-specified procedure. Any worsening (i.e., any clinically significant adverse change in frequency and/or intensity) of a preexisting condition that is temporally associated with the use of (⁸⁹Zr-)pembrolizumab, is also an adverse event.

Changes resulting from normal growth and development that do not vary significantly in frequency or severity from expected levels are not to be considered adverse events. Examples of this may include, but are not limited to, teething, typical crying in infants and children and onset of menses or menopause occurring at a physiologically appropriate time.

Adverse events may occur during the course of the use of (⁸⁹Zr-)pembrolizumab in clinical trials or within the follow-up period specified by the protocol, or prescribed in clinical practice, from overdose (whether accidental or intentional), from abuse and from withdrawal. Adverse events may also occur in screened subjects during any pre-allocation baseline period as a result of a protocol-specified intervention, including washout or discontinuation of usual therapy, diet, placebo treatment or a procedure.

Progression of the cancer under study is not considered an adverse event unless it is considered to be drug related by the investigator.

All adverse events will be recorded from the time the consent form is signed through 90 days following cessation of treatment or the initiation of new anti-cancer therapy, whichever is earlier and at each examination on the Adverse Event case report forms/worksheets. The reporting timeframe for adverse events meeting any serious criteria is described in section 7.2.3.1.

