8.0 STATISTICAL ANALYSIS PLAN

8.1 Safety

Safety of the combination of SBRT and pembrolizumab will be assessed by the percentage of ≥ 3 pneumonitis. When combined SBRT and pembrolizumab treatment results in NCIC-CTC grade ≥ 3 pneumonitis in $\leq 10\%$ of patients, the combination is regarded as safe.

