10.3.5 Safety of the trimodality approach

Combining SBRT with surgery appears safe. At least 4 small studies have reported on patients who have undergone surgery for salvage in patients who have recurred after SBRT (42-45). Since the results of SBRT seem to be equivalent to those of surgery we believe that the delay to surgical resection is not harmful and might even be beneficial for patients. The addition of pembrolizumab to SBRT might lead to a higher rate of pneumonitis. However, the incidence of pneumonitis depends on the target volume and is rarely seen with treatment of early stage lung cancer. Because only patients with peripheral tumors are eligible for this trial and patients receive a lobectomy according to national guidelines on the treatment for NSCLC, the irradiated lung lobe will be resected and resection margins (i.e. central bronchial and vascular structures) are not involved in the radiation target volume.

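### The section 8.1 pneumonitis percentage describes SBRT + pembrolizumab followed by lobectomy, so it cannot by itself support calling the combination safe without resection

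*Combined protocol and SAP*

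**What the plan says.** - **The rule.** Section 8.1: "Safety of the combination of SBRT and pembrolizumab will be assessed by the percentage of" grade 3 or higher pneumonitis. If this is 10% or less, "the combination is regarded as safe". The section gives no assessment window and no denominator, and does not say how lobectomy is handled.
- **The sign behind it.** Section 4.2.4: "The endpoints will be assessed by clinical signs of" radiation pneumonitis, among other assessments. The same section gives 10 patients per arm.
- **The target.** Objective 1 in section 3.1 names SBRT and pembrolizumab only. Sections 2.1, 4.2.1 and 4.2.4 instead describe the safety of the three-part regimen including surgery.
- **The surgery.** The flow chart in section 6.1 schedules it "From day 56 to day 70".
- **What surgery removes.** Section 10.3.5: "the irradiated lung lobe will be resected and resection margins" lie outside the radiation target volume. Section 4.1.7 uses the removal as an argument: "because the irradiated tumor and surrounding lung tissue are resected with the lobectomy, we do not foresee increased toxicity".
- **Adverse event recording.** Section 7.2 records events "through 90 days following cessation of treatment", or to new anti-cancer therapy if earlier. Section 5.10 gives 30 days after the end of treatment. Section 7.1.5.3.1 places the safety visit about 30 days after the last dose. The flow chart ticks adverse event review for screening and induction only.
- **Replacement.** Section 5.11 replaces patients who do not receive all three treatments.

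**The concern.** The conclusion in 8.1 is attached to a two-part combination, but the data come from a three-part regimen whose third part removes the high-dose lung. From lobectomy onwards a patient can no longer develop pneumonitis in that lung and, if event-free until then, adds nothing to the numerator from that source. The protocol itself counts on this removal when it argues that no extra toxicity is expected. A low percentage therefore cannot show that SBRT plus pembrolizumab would be equally safe with the lobe left in place.

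This is the only numerical criterion for a primary objective. Section 4.2.1 looks ahead to further work in early stage lung cancer and in stage III disease, which it calls "a setting where radiation pneumonitis is a well-known and feared complication". A statement that the combination is safe could easily be read as applying there.

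**Working it through.** **1. Timeline.** With dosing every 3 weeks, dose 2 falls on day 1 + 21 = 22 and cycle 2 ends on day 42. Adding 14 days gives day 56, and weeks 8 to 10 from the start of SBRT are days 56 to 70. This reproduces the flow chart. Section 5.6.3 leaves the starting point of its 8 to 10 weeks open. A later starting point moves the cut-off but not the argument.

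**2. Where the adverse event periods end, relative to lobectomy on day 56–70.**

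| Treatment taken to end at | +30 days | +90 days |
|---|---|---|
| Last dose, day 22 | day 52 (4–18 days before) | day 112 (42–56 days after) |
| End of cycle 2, day 42 | day 72 (2–16 days after) | day 132 (62–76 days after) |
| Surgery, day 56–70 | day 86–100 (30 days after) | day 146–160 (90 days after) |

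On one reading routine recording stops before surgery. On the others it runs past it.

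**3. Does the length of the period matter?** The measure is patients with an event divided by patients. Extra days without risk in the resected lung change neither number. Only a rate per person-time would be diluted (56/112 = 0.50 to 70/112 = 0.63), and 8.1 does not use one. Any understatement comes from surgery cutting off the risk.

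**4. Direction.** Let R be the risk of grade 3 or higher pneumonitis without resection, s the share arising in the lung that is removed, and f the share of those events that start before lobectomy. Assume that surgery does not itself change pneumonitis in the remaining lung and that all events are recorded. Then

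expected percentage = R × [1 − s(1 − f)].

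This equals R if f = 1 or s = 0, and is below R otherwise. The documents give none of R, s or f.

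**5. Effect on the rule (illustration).** With 10 patients, 10% or less means at most 1 event, so P(called safe) = (1 − p)^10 + 10p(1 − p)^9.

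Assumed R = 20%:

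| s | f | Expected percentage | P(called safe) |
|---|---|---|---|
| any | 1 | 20% | 0.376 |
| 1 | 0.75 | 15% | 0.544 |
| 1 | 0.5 | 10% | 0.736 |
| 1 | 0.25 | 5% | 0.914 |
| 0.5 | 0.75 | 17.5% | 0.456 |
| 0.5 | 0.5 | 15% | 0.544 |
| 0.5 | 0.25 | 12.5% | 0.639 |

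At an assumed R of 5%, halving the visible risk to 2.5% moves the probability only from 0.914 to 0.975.

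**6. Who is counted.** Suppose one patient misses surgery because of pneumonitis and is replaced, and one of the 10 who complete also has an event. Dropping the replaced patient gives 1/10 = 10%, which meets the rule. Keeping that patient gives 2/11 = 18%, which does not. Section 8.1 does not say which applies.

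**The case against.** The strongest reply is that lobectomy is protocol treatment in both arms. Sections 2.1, 4.2.1 and 4.2.4 make the three-part regimen the safety target, and for that target a lower pneumonitis risk after resection is part of the true risk. This stands: there is no bias for the regimen under study. It does not rescue the wording of Objective 1 and 8.1, which leave surgery out.

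Other parts of the reply also stand:

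- **Size.** Section 4.1.7 calls pneumonitis rare after treatment of early stage disease and cites 1.8% with pembrolizumab in a phase I trial. At low risk the effect on the rule is small, and no onset times are given.
- **Remaining lung.** Section 5.4.1 maps dose regions across the ipsilateral lung and one in the contralateral lung. Pneumonitis in remaining irradiated lung, and drug pneumonitis, can still occur after surgery.
- **Other measures.** CT density before surgery (5.4.1, 8.4) and histology of the resected lobe (8.2.1) capture injury in the irradiated lung, although they do not replace clinical grading.

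A reader might also infer that section 4.2.1 plans to carry the pneumonitis rate over to stage III disease. It does not: it speaks of proof of principle for the immunological effect and of a possible basis for later development.

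**Conclusion.** The point holds as a mismatch between the claim and what is measured. The percentage estimates the risk for SBRT plus pembrolizumab followed by lobectomy. For the combination without resection it can only equal or understate the risk, given the assumptions in step 4. The amount cannot be fixed from the documents and may be zero. The change from 0.38 to 0.74 rests on an assumed 20% risk, all of it in the resected lung, with half starting before surgery.

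Two stronger readings are tempting and are not supported. One is that a long adverse event period after surgery dilutes the percentage: 8.1 names no period, the other sections disagree on it, and a patient-level percentage is not diluted by added days. The other is that the understatement can be sized from the plan's own days, as 38–50% (one minus the ratios in step 3). That would need a constant hazard ending on day 112, which is a recording limit under one reading and not an onset distribution.

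**What to change.** In section 8.1:

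1. Limit the conclusion to SBRT + pembrolizumab followed by lobectomy at 8–10 weeks, and state that it does not apply to the combination without resection. Align Objective 1 with this.
2. Report grade 3 or higher pneumonitis separately from first treatment to each patient's actual lobectomy date, and after lobectomy. A fixed day 56 would misplace events on days 56 to 70 in patients not yet resected.
3. Keep every patient who started the combination in the numerator and denominator, including those not resected and replaced under 5.11.
4. Reconcile the adverse event periods in sections 5.10, 6.1, 7.1.5.3.1 and 7.2 so that recording covers both periods.

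A matching qualifier in section 4.2.1 is optional.

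The cost is a narrower safety claim, protocol and SAP wording, and one extra table. If adverse event review is in practice confined to the visits ticked in the flow chart, item 4 also adds data collection after surgery.

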5.2 Sample size

Twenty patients will be included in this study. A formal power analysis to calculate a sample size is not feasible due to the explorative nature of this trial. The sample size of 10 patients in each arm is based on two previous analyses that we performed. In a cohort of 9 head and neck cancer patients we were able to find significant differences in the expression of activation markers between different dendritic cell subsets (data on file). In a cohort of 9

melanoma patients we were able to find significant differences in the expression of activation markers between dendritic cell subsets of patients with a Breslow thickness more or less than 1.5 mm (60).

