5.6.2.1 Dose Modification

Pembrolizumab will be withheld for drug-related Grade 4 hematologic toxicities, non-hematological toxicity ≥ Grade 3 including laboratory abnormalities, and severe or life-threatening AEs as per Table 3 below.

Table 3: Dose modification guidelines for drug-related adverse events.

Toxicity	Hold Treatment For Grade	Timing for Restarting Treatment	Treatment Discontinuation
Diarrhea/Colitis	2-3	Toxicity resolves to Grade 0-1	Toxicity does not resolve within 12 weeks of last dose or inability to reduce corticosteroid to 10 mg or less of prednisone or equivalent per day within 12 weeks
	4	Permanently discontinue	Permanently discontinue
AST, ALT, or Increased Bilirubin	2	Toxicity resolves to Grade 0-1	Toxicity does not resolve within 12 weeks of last dose
	3-4	Permanently discontinue (see exception below) ^a	Permanently discontinue

Toxicity	Hold Treatment For Grade	Timing for Restarting Treatment	Treatment Discontinuation
Type 1 diabetes mellitus (if new onset) or Hyperglycemia	T1DM or 3-4	Hold pembrolizumab for new onset Type 1 diabetes mellitus or Grade 3-4 hyperglycemia associated with evidence of beta cell failure	Resume pembrolizumab when patients are clinically and metabolically stable
Hypophysitis	2-4	Toxicity resolves to Grade 0-1. Therapy with pembrolizumab can be continued while endocrine replacement therapy is instituted	Toxicity does not resolve within 12 weeks of last dose or inability to reduce corticosteroid to 10 mg or less of prednisone or equivalent per day within 12 weeks
Hyperthyroidism	3	Toxicity resolves to Grade 0-1	Toxicity does not resolve within 12 weeks of last dose or inability to reduce corticosteroid to 10 mg or less of prednisone or equivalent per day within 12 weeks
	4	Permanently discontinue	Permanently discontinue
Hypothyroidism		Therapy with pembrolizumab can be continued while thyroid replacement therapy is instituted	Therapy with pembrolizumab can be continued while thyroid replacement therapy is instituted
Infusion Reaction	2 ^b	Toxicity resolves to Grade 0-1	Permanently discontinue if toxicity develops despite adequate premedication
	3-4	Permanently discontinue	Permanently discontinue
Pneumonitis	2	Toxicity resolves to Grade 0-1	Toxicity does not resolve within 12 weeks of last dose or inability to reduce corticosteroid to 10 mg or less of prednisone or equivalent per day within 12 weeks
	3-4	Permanently discontinue	Permanently discontinue

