5.10 Subject Withdrawal/Discontinuation Criteria

Subjects may withdraw consent at any time for any reason or be dropped from the trial at the discretion of the investigator should any untoward effect occur. In addition, a subject may be withdrawn by the investigator or the PI if enrollment into the trial is inappropriate, the trial plan is violated, or for administrative and/or other safety reasons. Specific details regarding discontinuation or withdrawal are provided in Section 7.1.3.

A subject must be discontinued from the trial for any of the following reasons:

- The subject or legal representative (such as a parent or legal guardian) withdraws consent.
- Confirmed radiographic disease progression
- Unacceptable adverse experiences
- Intercurrent illness that prevents further administration of treatment
- Investigator's decision to withdraw the subject
- The subject has a confirmed positive serum pregnancy test
- Noncompliance with trial treatment or procedure requirements
- The subject is lost to follow-up
- Administrative reasons

The End of Treatment and Follow-up visit procedures are listed in Section 6 (Trial Flow Chart) and Section 7.1.4 (Visit Requirements). After the end of treatment, each subject will be followed for 30 days for adverse event monitoring. Subjects who discontinue for reasons other than progressive disease will have post-treatment follow-up for disease status until disease progression, initiating a non-study cancer treatment, withdrawing consent or becoming lost to follow-up.

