5.11 Subject Replacement Strategy

Subjects that fail to undergo the trimodality treatment will be replaced.

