7.1.2.10 Immunophenotyping on peripheral blood

To evaluate the pre- and on-treatment immune status, polychromatic flowcytometric analyses of lymphoid and myeloid subsets in peripheral blood will be performed at t = 0, 21 days (immediately prior to 2nd therapeutic dose), just before surgery, one week after surgery and after 6 months. Heparinized blood (40 ml) will be taken at each of these time points and PBMC isolated. The following 8-12 marker panels will be run on a BD LSRFortessa (with appropriate FMO controls): 1) Treg/effector T cell activation panel: CD3, CD4, CD8, CD25, CD127, CD45RA, Ki67, FoxP3, HLA-DR, CTLA-4, PD-1, CD27; 2) Dendritic cell panel:

CD1c/BDCA-1, CD202/BDCA-2, CD141/BDCA-3, M-DC8 (Sulph-LacNac), CD14, CD11c, CD16, CD19, CD40, CD80, PD-L1; 3) Myeloid-derived suppressor cell panel: CD11b, CD14, CD33, CD3/19/56 (Lin), HLA-DR, CD15, CD16, PD-L1. By performing these analyses at the indicated time points, we will gain unique insight in the kinetics of T cell activation following SBRT and PD-1 blockade and pre-, on- and post-treatment immune effector/suppressor subset profiles that may show differences between the two treatment arms, as we previously showed in a trial of combined ipilimumab and Prostate GVAX immunotherapy (76-78).

7.1.2.11 Ultrasound endoscopy guided cytological lymph node aspiration for immunological cell composition (EBUS FACS)

Patients will undergo an EBUS-FNA of the ipsilateral and contralateral hilar and mediastinal lymph nodes within 2 weeks before and between week 2 and 3 after SBRT (see section 5.4).

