7.1.3 Withdrawal/Discontinuation

When a subject discontinues/withdraws prior to trial completion, all applicable activities scheduled for the final trial visit should be performed at the time of discontinuation. Any adverse events which are present at the time of discontinuation/withdrawal should be followed in accordance with the safety requirements outlined in Section 7.2 - Assessing and Recording Adverse Events.

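### Section 8.1 declares the combination safe at 0 or 1 severe pneumonitis cases in 10 patients, with no confidence limit and no rule for counting replaced patients

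*Combined protocol and SAP*

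**What the plan says.** Section 3.1 makes the safety of combined SBRT and pembrolizumab the first primary objective. Section 8.1 is its whole analysis: if grade 3 or higher pneumonitis is seen in no more than 10% "of patients, the combination is regarded as safe". It names no interval, error rate, analysis set or observation period. The only other criterion, in Section 5.13, is a qualitative reason for early termination.

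On numbers, Section 5.2 states: "The sample size of 10 patients in each arm is based on two previous analyses that we performed". Those two analyses concerned dendritic-cell markers, not safety.

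On who is counted, Section 5.11 states: "Subjects that fail to undergo the trimodality treatment will be replaced". In Section 5.6.2.1 ("Table 3: Dose modification guidelines for drug-related adverse events"), the pneumonitis row ends pembrolizumab permanently at grade 3-4. Section 5.10 lists unacceptable adverse experiences as a reason for discontinuation from the trial.

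Events in patients who leave are not lost from the record. Section 7.1.3 says: "Any adverse events which are present at the time of discontinuation/withdrawal should be followed". But no section says whether these patients enter the Section 8.1 percentage.

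On time, Section 5.10 says: "After the end of treatment, each subject will be followed for 30 days for adverse event monitoring". Section 7.2 says: "All adverse events will be recorded from the time the consent form is signed through 90 days following cessation of treatment", or until new anti-cancer therapy if that is earlier.

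**The concern.** The rule turns a point estimate from 10 patients into a categorical conclusion on a primary objective. Section 10.3.5 accepts that adding pembrolizumab might raise the pneumonitis rate. Section 2.1 places this trial ahead of larger studies, and Section 4.2.1 looks towards stage III disease, where it describes radiation pneumonitis as a feared complication. If Section 8.1 is followed as written, the trial could report its safety objective as met on data that cannot exclude a high rate of severe pneumonitis.

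The replacement rule adds a second, conditional problem. The event being counted can itself lead to discontinuation and replacement. If replaced patients were left out of the percentage, the rate would be computed in a group selected partly for not having the event.

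**Working it through.** **Inputs.** Threshold of at most 10% (8.1); 10 patients in the combination arm (4.2.4, 5.2); replacement rule (5.11); pneumonitis rate of 1.8% on pembrolizumab alone, grade not clearly stated (4.1.7); second dose at "21 days (immediately prior to 2nd therapeutic dose" (7.1.2.10); surgery on days 56 to 70 (6.1). The plan gives no alpha, power or interval, so it has no figure to reproduce. The 95% level is my choice. True rates other than 1.8%, and all replacement shares, are illustrative assumptions.

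**1. The rule in counts.** 0.10 × 10 = 1, so the rule passes at 0 or 1 event.

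**2. What a passing result excludes.** Exact (Clopper-Pearson) two-sided 95% intervals:
- 0/10: 0 to 1 − 0.025^(1/10), that is, 0 to 30.8%.
- 1/10: 0.3% to 44.5%.

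Other upper limits for 1/10 are 39.4% (one-sided 95% exact), 33.7% (one-sided 90% exact) and 40.4% (Wilson 95%). For zero events to give a two-sided 95% upper limit below 10%, n must exceed ln(0.025)/ln(0.9) = 35.01, so 36 patients. A one-sided 95% limit needs 29.

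**3. How often the rule passes.** P(X ≤ 1) = (1−p)^10 + 10p(1−p)^9:

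| True rate p | P(declared safe) |
|---|---|
| 1.8% | 0.987 |
| 5% | 0.914 |
| 10% | 0.736 |
| 15% | 0.544 |
| 18% | 0.439 |
| 20% | 0.376 |
| 25% | 0.244 |
| 30% | 0.149 |

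**4. Replaced patients kept.** With 11 or 12 treated patients, one event is still the most that passes. At p = 20%, P(X ≤ 1) is 0.322 for n = 11 and 0.275 for n = 12. Replacement then does not raise the chance of passing.

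**5. Replaced patients dropped.** Let a share q of cases and a share r of non-cases be replaced. The rate among the 10 retained is p(1−q) / [p(1−q) + (1−p)(1−r)]. At p = 20%:

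| q | r | Retained rate | P(declared safe) |
|---|---|---|---|
| 0.25 | 0 | 0.15/0.95 = 0.158 | 0.516 |
| 0.50 | 0 | 0.10/0.90 = 0.111 | 0.693 |
| 0.25 | 0.10 | 0.15/0.87 = 0.172 | 0.465 |
| 0.50 | 0.10 | 0.10/0.82 = 0.122 | 0.651 |

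The verdict can also flip on a single case. One event in a replaced patient and one among 10 completers is 1/10 (passes) on completers, but 2/11 = 18.2% (fails; exact 95% CI 2.3% to 51.8%) on all treated.

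**6. Window.** The end date depends on what ends treatment:

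| Treatment ends at | 30 days ends | 90 days ends |
|---|---|---|
| Second dose, day 21 | day 51 | day 111 |
| End of second cycle, about day 42 | day 72 | day 132 |
| Surgery, days 56-70 | days 86-100 | days 146-160 |

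The day-42 reading follows from the flow chart in Section 6.1, which places day 56 two weeks after the second cycle. On the first reading, the 30-day period closes before surgery begins.

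**The case against.** **The standard is imported.** The trial is exploratory, Section 5.2 says a formal power analysis is not feasible, and no section requires an upper limit below 10%. Section 8.1 could be read as a simple benchmark, and it does discriminate: it passes 99% of the time at 1.8% and 15% at 30%. It is true that 44.5% is the largest of the limits computed and that the level is my choice. But every variant for 1/10 is above 33%. An exploratory design excuses the missing power calculation; it does not support a categorical verdict.

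**The replacement bias is not shown.** Section 8.1 refers to the two-part combination, not surgery, so its natural denominator is everyone given that combination. A patient who had SBRT, one dose and surgery may not need replacing, and stopping pembrolizumab after the second dose withholds nothing that was planned. This stands: the bias is conditional, and the shares in step 5 are assumptions. The gap in the text remains, and missed surgery or discontinuation under Section 5.10 is still a route to replacement.

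**Ninety days is the clearer rule.** Section 7.2 and the serious-event rules in Section 7.2.3.1 use it, while 30 days matches the safety follow-up visit, after which events above grade 1 are followed further. That is fair, but Section 5.10 still conflicts with it and Section 8.1 names neither period.

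**Section 8.1 is not a go/no-go rule, and readers could compute an interval themselves.** Both are true, but neither justifies reporting a conclusion the data cannot support.

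**Conclusion.** The concern holds. Followed exactly, Section 8.1 would report a primary objective as met on 0/10 or 1/10, results compatible at 95% confidence with true rates up to 30.8% and 44.5%. At a true 20% it passes 38% of the time. This rests only on the stated threshold and arm size, and no standard interval method brings the upper limit for 1/10 near 10%.

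The denominator and window are real omissions, but ambiguities rather than demonstrated bias. At an assumed true 20%, P(declared safe) runs from 27% (two replaced patients kept, n = 12) to 69% (half of cases replaced and dropped). The main conclusion does not depend on either omission.

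**What to change.** 1. **Section 8.1, conclusion.** Replace the safety verdict with: *The proportion with grade ≥3 pneumonitis will be reported with its exact (Clopper-Pearson) 95% confidence interval, with a statement of which rates the upper limit does and does not exclude.* The 10% figure may stay as a descriptive reference, provided no verdict hangs on it.
2. **Sections 5.11 and 8.1, denominator.** State that replacement serves the translational analyses only, and that the pneumonitis rate is computed in all patients who start SBRT plus therapeutic pembrolizumab, including those later discontinued or replaced. Section 5.3.2.3 removes patients with an allergic reaction to the tracer. Report those reactions separately, and do not add patients who received only the tracer to this denominator.
3. **Sections 5.10, 7.2 and 8.1, window.** Reconcile the 30 and 90 days, say which event ends treatment, and name the resulting window in Section 8.1 so that events in replaced patients are captured.

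The cost is wording in four sections, with no extra patients. The price is a less favourable safety statement and possibly a denominator above 10.
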